3.3.3 Study Data Collection

All participants of the NAC trial must first be enrolled in the PALF registry and therefore all data collected as part of the registry will be available for these patients. Additional data collected for the NAC trial include:

- A form listing the patient's match to inclusion/exclusion criteria
- A daily log to capture the date and time infusion was started, the amount of the intravenous infusion, clinical measures, and adverse events. The date of treatment allocation, patient's weight and coma grade are also recorded on the log.

The daily log will be faxed upon completion to the DCC.

A parent may withdraw consent for participation in this research study at any time. In addition, a site principal investigator may withdraw a child from the study in circumstances related to either the parent or child's failure to cooperate fully with the conduct of the study, or the recognition of significant medical risks associated with the child's continued participation in this study. If a child's participation in this study is stopped, the reasons will be discussed with the parents and the child. Any research or medical information recorded for, or resulting from, the child's participation in this research study prior to the date that consent for child's participation was formally withdrawn may continue to be used by the investigators for the purposes described above.

3.3.4 Biospecimen Collection

No additional samples will be collected for participants who are enrolled into this trial on the same day that they are enrolled in the PALF registry, since the registry includes the collection of daily samples for 7 consecutive days. If for some reason the patient is enrolled in this trial at least one day after entry into the registry, blood samples will be collected for up to 7 days following enrollment in this trial. The maximum blood volume collected over the 7 day period will not exceed the maximum whole blood volume for a single blood draw or the cumulative volume, as stated in the clinical centers IRB guidelines.

3.3.5 Statistical Analysis

The primary outcome for this study is to compare survival at one year (with or without transplantation) for patients in the two treatment arms. Due to potential missing data, survival techniques to account for censored data will be used. Product-limit estimates of survival for the two treatment arms will be compared using a log-rank test.

In addition, demographic and patient characteristics will be analyzed for trends. Two proportion comparisons or Chi Square contingency table analyses will be performed when the data to be compared are from 2 x 2 tables (e.g. gender by year 1997 vs. 1999). When the data are measured at several different levels (e.g. race) across two or more years, the Cochran-Armitage Test for Trend or Jonckheere-Terpstra Test will be performed. To examine the association in these tables, Phi or Cramer's V will be utilized for 2 x 2 or higher way tables. If the data have ordered categories, Goodman and Kruskal's Gamma (G) is appropriate.

Univariate statistical analyses will be performed for each of the patient demographic and illness characteristics at baseline for descriptive purposes and to determine their possible relationship with the primary outcome. Baseline characteristics will be compared between patients in the two treatment arms to determine whether treatment allocation balanced the groups with respect to measured variables. Chi square analysis will be used to examine group differences for dichotomous variables, independent group Student t-tests will be performed for normally distributed, continuous variables, and Mann-Whitney U tests for the other continuous measures.

Cox's proportional hazards regression model will be used to model the primary outcome and secondary outcomes of spontaneous survival and transplantation rate. The predictor variables in each of the equations will include the variables used in the minimization scheme (age, coma score). In addition, analyses will examine whether treatment effect changes when adjusting for a measure of patient illness, e.g., number of organ systems failing at baseline, APACHE II, or King's criteria.

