3.2 Research Design and Methods

N-acetylcysteine is being tested in a double blind, placebo-controlled, randomized trial as a treatment for non-acetaminophen ALF in children. The study drug or placebo will be given as a 7 day continuous intravenous infusion to children with acute liver failure not due to acute acetaminophen toxicity.

Vials of NAC will be available at each clinical center in the research pharmacy. Upon identification of a patient, study personnel (investigator or coordinator) will obtain informed consent, and then notify the research pharmacist of the patient's body weight, coma grade, and age. Orders for the solutions and the informed consent will be submitted to the clinical center's pharmacy, confirming that the patient is part of the study and outlining the timing for the infusion. The pharmacist will then log onto a web-based treatment allocation system maintained at the DCC which assigns therapy using a minimization scheme designed to balance treatment groups within a site by age (less than 2 years vs. at least 2 years) and coma score (0,1 vs. 2-4). The research pharmacist will prepare either a NAC solution as outlined below or 5% dextrose (placebo). The N-acetylcysteine will be added to 5% dextrose. The solution containing N-acetylcysteine will be administered as a continuous infusion at a dose of 150 mg/kg bodyweight in 5% dextrose over 24-hours for 7

consecutive days. Volumes will be adjusted for small children. The solution will be delivered to the clinical center with study labels which do not disclose the specific contents. Patients allocated to placebo will receive volume-matched 5% dextrose infusions. The NAC solution is colorless, so there should be no difficulty with inadvertent product identification. It may be possible to identify the solution by its smell, but all reasonable efforts will be made to exclude investigators from awareness of this information. A standard order form for the infusions will be inserted in the patient's chart to provide uniform orders at the study onset. Infusion of the study solution should take place as soon as possible following study entry (consent signed).

Participation in the NAC trial will not interfere with standard treatment for ALF including liver transplantation, if it is considered appropriate.

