3.3 Data Collection and Statistical Considerations

3.3.1 Sample Size Calculation:

It is anticipated that 90 children with PALF will be admitted to the clinical centers each year. Of those, approximately 20% will likely be due to acetaminophen overdose leaving 72 patients eligible for the study. We anticipate 25% of the eligible patients will not be enrolled, leaving an estimated 54 patients per year to be randomized. The one year death rate without transplant of 15% is lower than in the adult population. However, while a greater percentage of children receive a liver transplantation (40%), 40% of these children die, leaving an estimated overall survival with or without a liver transplant of 69% in the placebo arm. See diagram provided in Appendix 1 on page 20.

Based on these data, the estimated sample size to evaluate the efficacy of IV-NAC in the treatment of ALF in children was calculated. The original sample size was calculated assuming a one year survival rate for the patients in the treatment arm is 86.5% and 6 planned interim analyses. This comparison would need 92 patients in each arm (184 total) to achieve 80% power (likelihood of rejecting the hypothesis of equal survival rates) with a two-sided test of survival (log-rank test) at $\alpha=0.054$. The external Data and Safety Monitoring Board has accepted a revised interim monitoring plan for efficacy consisting of a single interim analysis when half of the sample of 184 reaches the one-year follow-up. Keeping the sample size at 184, this effectively lowers the type I error to 0.05 while maintaining 80% power.

Due to preliminary findings in a similar study, an additional interim analysis was performed. There will be 3 looks at the data; the first when 79 participants are enrolled (which was shown to the DSMB on August 30, 2007) among whom 42 participants were enrolled on or before July 1, 2006, i.e., enrolled for at least 1 year, the second when 92 participants reach the 1 year follow-up and the last when all 184 participants reach the 1 year follow-up.

With this revised plan, the power remains at 85%. The new O'Brien-Fleming boundaries will be:

- 4.550, 4.550 corresponding to a nominal α of 0.00005 at the first look
- 2.963, 2.963 corresponding to a nominal α of 0.00305 at the second look
- 1.969, 1.969 corresponding to a nominal α of 0.04900 at the third look

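### The log-rank test that carries the alpha ignores age and coma score, on which allocation is minimized; if these factors are prognostic, the test is mildly conservative and gives up a few points of power

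*Protocol*

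**What the plan says.** Protocol 3.2 describes "a minimization scheme designed to balance treatment groups within a site by age (less than 2 years vs. at least 2 years"). The second factor is "coma score (0,1 vs. 2-4").

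Protocol 3.3.5 fixes the primary comparison: "Product-limit estimates of survival for the two treatment arms will be compared using a log-rank test". It mentions neither strata nor covariates for this test. Sections 3.3.1 and 6.2 base the 184 children on a two-sided log-rank test, and 6.2 ties the O'Brien-Fleming boundaries to it. The revised boundaries in 3.3.1 and 3.3.6 name no other test.

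Section 3.3.5 also plans a second analysis: "Cox's proportional hazards regression model will be used to model the primary outcome and secondary outcomes of spontaneous survival and transplantation rate". For these models it adds: "The predictor variables in each of the equations will include the variables used in the minimization scheme (age, coma score"). Site is named in neither analysis, although the minimization works within site.

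**The concern.** Minimization makes the arms more alike on age and coma score than chance would. If those factors predict death, the treatment difference varies less between hypothetical repetitions of the trial than the unstratified log-rank variance assumes, so its p-values tend to be too large. Separately, pooling children of unequal risk pulls the unstratified comparison towards no effect. That second mechanism costs power even under simple randomization.

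At stake is efficiency. The design expects about 41 deaths in a rare disease, so a few points of power obtainable from data already recorded at allocation are worth having. There is also an ambiguity: the section plans two treatment comparisons of the primary outcome, one ignoring the allocation factors and one using them. If they fall on either side of the final boundary of 1.969, the unadjusted one appears to decide.

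**Working it through.** **Inputs from the protocol.** Placebo one-year survival 0.69 and NAC 0.865 (3.3.1, 6.2); 92 per arm; 20 centers (Introduction); final boundary 1.969, nominal alpha 0.049 (3.3.6).

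**Reproducing the plan's own figures.**
- Hazard ratio under proportional hazards: ln(0.865)/ln(0.69) = 0.391.
- Expected deaths: 92 × 0.31 + 92 × 0.135 = 28.5 + 12.4 = 40.9.
- Freedman's formula, ((1 + HR)/(1 − HR))² × (1.960 + 0.842)², gives 41 deaths. The average death probability is (0.31 + 0.135)/2 = 0.2225, so N = 41/0.2225 ≈ 184. This matches the plan at alpha 0.05 and 80% power.
- Schoenfeld's formula gives √(40.94/4) × |ln 0.391| = 3.006, hence power of 85.2% at alpha 0.05. This matches the 85% quoted for the three-look plan.

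The powering is therefore that of a plain log-rank test on marginal survival rates.

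**Simulation of the mismatch.** 184 children, 20 centers, biased-coin minimization within center on age and coma score, exponential survival, follow-up to one year. Marginal survival is held at 69% vs 86.5%. Rejection is at |Z| > 1.969 at the final look only. Assumptions not in the protocol: the prognostic hazard ratios, 35% and 30% of children in the higher-risk age and coma groups, independence of the two factors, coin probability 0.8, equal expected center sizes, no dropout. There are 15,000 runs per row.

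| Assumed HR, age / coma | Type I error, unstratified | Type I error, stratified | Power, unstratified | Power, stratified |
|---|---|---|---|---|
| 1.5 / 1.5 | 0.047 | 0.049 | 82.8% | 82.3% |
| 1.5 / 2 | 0.045 | 0.049 | 82.5% | 83.0% |
| 1.5 / 3 | 0.043 | 0.047 | 83.0% | 85.4% |
| 2 / 4 | 0.040 | 0.050 | 83.6% | 87.7% |
| 3 / 6 (extreme) | 0.030 | 0.050 | 84.6% | 91.8% |

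Monte Carlo standard error is about √(0.049 × 0.951/15,000) = 0.002 for type I error and √(0.83 × 0.17/15,000) = 0.3 points for power. Differences in the first row are therefore not meaningful.

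**Sensitivity to the algorithm, which the protocol does not give (12,000 runs).** With deterministic minimization, unstratified type I error is 0.043 (1.5/2), 0.038 (1.5/3) and 0.034 (2/4), and the power gaps are 0.4, 1.9 and 3.9 points. With pure coin-tossing it is 0.047, 0.050 and 0.050, but the power gaps remain at 0.4, 2.9 and 4.3 points. So the conservatism comes from the minimization, while the power gap comes mainly from ignoring prognostic factors.

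**Room for strata.** Four strata from age and coma score are workable at the final look, at about 41/4 ≈ 10 deaths each on average. Among the 92 children of the second look, about 46 × 0.31 + 46 × 0.135 = 20.5 deaths are expected, or roughly five per stratum. Site is a different matter: 184/20 ≈ 9 children per center.

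**The case against.** The case for leaving the test alone has several parts.

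- *The protocol never says unstratified, and a SAP may settle it.* This is fair up to a point. But 3.3.5 names the allocation factors for the Cox models and not for the test, so the text reads as a choice. If a SAP already stratifies, only the protocol wording needs aligning.
- *An adjusted analysis is already planned.* True. A reader might infer that the plan throws away age and coma score; it does not, since the Cox model of the primary outcome uses both. What remains is that the test tied to the alpha and sample size uses neither.
- *Nothing shows that the factors are prognostic.* This stands. The remark in 2.1.1 that prognosis may depend on age is qualitative and sits in a paragraph on adults. With weak factors the tests are equivalent.
- *The trial may fall short of its power.* A reader might infer this, and a scenario can be built for it. Four equal strata with placebo survival of 92/82/62/40% and HR 0.391 within each give 79.3% unstratified against 84.1% stratified (8,000 runs, early deaths, critical value 1.96). But the hazards there differ by ln(0.40)/ln(0.92) ≈ 11-fold, and mean NAC survival is about 85.5% instead of 86.5%. Part of the shortfall is a smaller treatment effect. With the planned marginal rates held, no scenario falls below 82%.
- *Minimization is within site, yet the remedy leaves site out.* This is a real inconsistency of principle, justified by the small number of children per center.

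**Conclusion.** The mismatch is real and modest. If age group and coma group have moderate to strong effects on survival (assumed hazard ratios from 1.5/2 to 2/4), the unstratified log-rank runs at about 0.045 to 0.040 against a nominal 0.049 and forgoes roughly half a point to 4 points of power against a stratified test. An extreme assumption (3/6) gives 0.030 and about 7 points. With weak factors there is no measurable difference.

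A reader might conclude that the primary test is invalid or the trial underpowered. Neither follows: the type I error departs only on the safe side, and unstratified power is 82-85% in every scenario that keeps the planned survival rates. The sizes rest on prognostic effects and a minimization algorithm that the protocol does not state, and on the final look alone. The change is worthwhile, but the design does not depend on it.

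**What to change.** In 3.3.5, make the primary test at the remaining looks a log-rank stratified by age (under 2 vs 2 years or more) and coma score (0-1 vs 2-4). Alternatively, name the treatment test from the planned Cox model adjusted for these factors as primary. Keep the unstratified log-rank as a sensitivity analysis. State that site is not a stratification factor, because there are only about 9 children per center.

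No new data are needed, since both factors are recorded before allocation. The costs are small but not nil. The DSMB reviewed the first look on August 30, 2007, so staff blinded to interim results should make the change, with its reasons documented before the second look. Strata will be sparse at that look, with about 20 deaths among the 92 children. If the factors prove weak, power may be up to about half a point lower than with the unstratified test.

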3.3.2 Endpoints of the study

Primary outcome measures:

1. Overall survival rate (spontaneous survival without transplant plus survival following transplantation) at one year following treatment allocation.

Secondary outcome measures:

1. Spontaneous survival (survival without transplantation)
2. Transplantation rate
3. Length of ICU and hospital stay
4. Number of organ systems failing:
 - a) Cardiovascular failure: defined as treatment with inotropic drugs: norepinephrine, epinephrine or dopamine (the latter $>5 \mu\text{g}/\text{kg}/\text{min}$), the terminal 24 h before death excluded.
 - b) Renal failure: defined as serum creatinine greater than 2 x the upper limit of normal for age and urine output less than 0.5 cc/kg/hour.
 - c) Intracranial hypertension: defined as intracranial pressure $> 25 \text{ mmHg}$ (if ICP monitored) or clinical signs of this condition (decerebrate posturing, abnormal pupillary reflexes).
 - d) Pulmonary support: defined as the need for mechanical ventilation for encephalopathy or respiratory failure, defined as an inspired oxygen fraction (FiO_2) above 0.40, the first 12 hours after intubation and the terminal 12 hours before death excluded. The FiO_2 criterion is important for the definition for two reasons: firstly, mechanical ventilation is used as a standard in the treatment of patients with cerebral edema to induce hyperventilation and thereby hypocapnia, and secondly, the medullary respiratory center may be depressed in patients with hepatic encephalopathy grade 4 and may thus cause a 'non-pulmonary' need for mechanical ventilation.
 - e) Infection: defined as detection of pathogenic microbial species in blood, tracheal, or urine cultures.
5. Degree of hepatic encephalopathy. The maximal hepatic coma grade (I - IV), and the number of days until recovery or death.

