32. Modig, J. and R. Sandin, *Haematological, physiological and survival data in a porcine model of adult respiratory distress syndrome induced by endotoxaemia. Effects of treatment with N-acetylcysteine*. Acta Chir Scand, 1988. **154**(3): p. 169-77.
33. Bailey, B. and M.A. McGuigan, *Management of anaphylactoid reactions to intravenous N-acetylcysteine*. Ann Emerg Med, 1998. **31**(6): p. 710-5.

NAC Study Protocol

6.2: Pediatric NAC Protocol

The overall survival rate at one year in this model is 69.0% (45.0% + 24.0%) in the placebo arm and 86.5% (55.0% + 31.5%). Estimating the total number of planned analyses at 6 using O'Brien Fleming boundaries for both H_0 and H_1 , a minimum of 184 patients (92 in each arm) will provide 80% power using a two-sided log-rank test (assuming proportional hazards) and an overall $\alpha = 0.054$ (if all 6 interim analyses are performed).

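### The only model named for transplantation rate is Cox regression, whose hazard ratio does not measure the proportion transplanted when death before transplant is common

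*Protocol*

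**What the plan says.** Section 3.3.2 of the protocol lists the endpoint as the second of five secondary outcomes, with no time point or further definition: "2. Transplantation rate".

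Section 3.3.5 chooses the model: "Cox's proportional hazards regression model will be used to model the primary outcome and secondary outcomes of spontaneous survival and transplantation rate". Each model is to include age and coma score, the two minimization variables. Censoring is mentioned once, in the paragraph on the primary outcome: "Due to potential missing data, survival techniques to account for censored data will be used". Product-limit estimates and the log-rank test appear in that same paragraph and are tied to the survival comparison. Competing events and cumulative incidence are not mentioned.

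The planning figures are in section 3.3.1: "The one year death rate without transplant of 15% is lower than in the adult population", and "while a greater percentage of children receive a liver transplantation (40%), 40% of these children die". Section 6.2 splits one-year overall survival into survivors without and with transplant: 45.0% + 24.0% on placebo and 55.0% + 31.5% on NAC.

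**The concern.** A child who dies without a transplant can no longer receive one, so death before transplant competes with transplantation. It is not missing data, which is the only reason for censoring that the protocol gives.

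The protocol uses the word rate for one-year proportions: the one-year overall survival rate, and the 15% death rate without transplant. Its planning model also treats transplantation as a percentage of children. A reader will therefore take transplantation rate as the proportion transplanted. The Cox model, in its usual form with prior deaths censored, answers another question: how fast transplants occur among children still alive and untransplanted.

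What is at stake is the statement the trial will make about whether NAC spares transplants. If the hazard ratio is the only result reported, it can suggest fewer transplants when the proportion is equal or higher.

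**Working it through.** **Inputs.** Placebo: 40% transplanted, 15% dead without transplant, 40% of transplanted children dying (section 3.3.1). NAC: 55.0% surviving without transplant, 31.5% surviving after transplant (section 6.2). Sample size: 92 per arm (section 3.3.1).

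**The plan's own figure.** Placebo survival without transplant is 1 − 0.40 − 0.15 = 0.45. Adding survivors after transplant, 0.40 × 0.60 = 0.24, gives 0.69, the stated 69%. So 40% and 15% are one-year proportions with a first event of transplant or death. The protocol gives no figure for the transplantation analysis itself.

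**Size of the competing event.** 0.15 / (0.15 + 0.40) = 15/55 = 27% of first events on placebo.

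**Range for NAC.** First events total 1 − 0.55 = 45%. At most all of them are transplants (45%). At least the 31.5% who survive after transplant must have been transplanted. The proportion transplanted therefore lies between 31.5% and 45%. The split within that range is an assumption.

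**Cause-specific transplant hazard.** If the two cause-specific hazards are proportional over the year, the cumulative transplant hazard is −ln(event-free proportion) × (transplanted / all first events).

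- Placebo: −ln(0.45) × 40/55 = 0.7985 × 0.727 = 0.581.
- NAC: −ln(0.55) × p/0.45 = 0.5978 × p/0.45, where p is the proportion transplanted.

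| NAC transplanted | NAC dead without transplant | Cause-specific HR | Ratio of proportions (NAC / 40%) |
|---|---|---|---|
| 31.5% | 13.5% | 0.72 | 0.79 |
| 35% | 10% | 0.80 | 0.875 |
| 40% | 5% | 0.915 | 1.00 |
| 42% | 3% | 0.96 | 1.05 |
| 45% | 0% | 1.03 | 1.125 |

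For the third row: 0.5978 × 40/45 = 0.531, and 0.531/0.581 = 0.915. For the fourth: 0.5978 × 42/45 = 0.558, and 0.558/0.581 = 0.96.

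**Where the two point in opposite directions.** The hazard ratio reaches 1 at p = 0.45 × 0.581/0.5978 = 43.7%. For any NAC proportion between 40% and about 43.7%, the hazard ratio is below 1 although more NAC children are transplanted.

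**Does a pure mortality effect distort the Cox result?** Leave the transplant hazard at 0.581 and halve the placebo death hazard, 0.7985 × 15/55 = 0.218, to 0.109. The cause-specific hazard ratio is 1.00 by construction (0.99 in simulation). The cumulative incidence of transplant becomes (0.581/0.690) × (1 − e^−0.690) = 42.0%, against 40.0% on placebo. Here the proportion moves and the Cox hazard ratio does not.

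**Set against sampling error.** About 0.40 × 92 = 37 transplants per arm give a standard error for the log hazard ratio of roughly √(1/37 + 1/37) = 0.23. The gap between 0.915 and 1.00 is −ln(0.915) = 0.089 on that scale, well under one standard error.

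**The case against.** The strongest reply is that nothing is wrong with the model. Cox regression with prior deaths censored is a standard, valid estimate of the cause-specific hazard ratio for transplant. This stands. A reader might infer that the Cox comparison is contaminated by any effect of NAC on mortality, or that it is biased in the example with 40% in both arms. The figures do not support either. An effect on the death hazard alone leaves the hazard ratio at 1.00; it is the cumulative incidence that moves. In the 40% example the NAC transplant hazard really is lower, 0.531 against 0.581, and 0.915 reports it correctly. The disagreement is between two quantities, not between a right and a wrong estimate of one.

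A reader might also infer that the proportions transplanted will be overstated. Censoring deaths in a Kaplan-Meier curve for transplant would turn the placebo 40% into 1 − e^−0.581 = 44.1%. But the protocol plans product-limit curves only for the primary outcome, so that error is not in the plan.

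Finally, the coding of deaths and any competing-risk summary may sit in a statistical analysis plan that is not at hand. That is fair, and silence on coding alone would not be a finding. What remains is that the protocol itself names the model, and names only one, for an endpoint that its own planning figures treat as a proportion.

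**Conclusion.** The point holds as a mismatch between endpoint and reported measure. The Cox hazard ratio alone does not compare the proportions transplanted. Over the range that section 6.2 allows for NAC, it runs from 0.72 to 1.03 while the ratio of proportions runs from 0.79 to 1.125, and the two point in opposite directions when between 40% and about 43.7% of NAC children are transplanted.

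These figures rest on three assumptions: prior deaths are censored, which is usual but not stated; cause-specific hazards are proportional over the year; and 55% survive without transplant under NAC, as planned. The planning diagram is not visible in the text available and may give the NAC split.

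The weight is moderate. The differences are small beside the sampling error of this trial, so the issue is what the result means rather than whether it reaches significance. The endpoint is secondary, and the log-rank test of overall survival and the sample size of 184 do not depend on it.

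**What to change.** In section 3.3.5, or in the statistical analysis plan with a cross-reference:

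- Compare transplantation between arms by cumulative incidence at one year after allocation, with death before transplant as a competing event, for example by Gray's test.
- Show the cumulative incidence of death without transplant by arm beside it.
- Keep the Cox model adjusted for age and coma score, state that children who die before transplant are censored at death, and label the result a cause-specific hazard ratio.
- Keep Cox regression for overall survival, and for spontaneous survival with death or transplant as the event.

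A Fine-Gray model with the same covariates is optional. Whether it or the cause-specific model should lead is a choice of estimand on which statisticians differ.

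The change needs no new data or patients, only wording and standard software. Its one drawback is two effect measures to explain instead of one.
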